## **10. STATISTICAL METHODS**

Statistical analysis will be performed by the sponsor or under the authority of the sponsor. A general description of the statistical methods to be used to analyze the efficacy and safety data is outlined below.

Specific details will be provided in the Statistical Analysis Plan (SAP).

## 10.1. Sample Size Determination

The sample size for this study is based on the assumption of a treatment difference of 3 points in the mean change from Baseline to Week 12 in PANSS negative subscale score based on the Marder negative factor score between any MIN-101 dose group and placebo. A standard

deviation of 6.5 in the change in PANSS negative subscale score from Baseline is used. Assuming an equal allocation to placebo and each of the 2 MIN-101 doses, 100 patients in each treatment arm are required to detect the treatment difference of 3 points with a power of 90% at an overall 2-sided significance level of 0.05. When adjusted for a rate of about 40% of patients who will not have either Baseline or at least 1 on-treatment efficacy assessments, the required number of patients becomes 167 in each treatment arm. Therefore, the total number of patients enrolled across the 3 treatment arms will be 501.

# 10.2. Data Sets

Three populations will be considered in the statistical analysis of the study:

**Intent-to-treat (ITT)**: This population will consist of all patients who were randomly assigned to study drug and received at least 1 dose of study drug.

Safety: This population will consist of all patients who were randomly assigned to study drug and received at least 1 dose of study drug. The safety analysis set is the same as the ITT.

**Per-protocol (PP): This population will include all patients in the ITT Population who do not present major protocol violations, i.e., violations thought to interfere with efficacy results such as erroneous diagnosis, insufficient compliance (< 80\%), or intake of prohibited concomitant medication. Major protocol violations will be identified before breaking the randomisation code.** 

Patients' assignment to analysis sets will be performed during the pre-analysis review meeting while the data remain blinded.

Taking into account the nature of this Phase 3 study, all efficacy analyses will be performed on both the ITT and PP sets, and eventual discrepancies between the results obtained in both sets will be discussed.

## 10.3. Patient Information

For all patients who received at least 1 dose of study drug, descriptive statistics by treatment arm, MIN-101 dose group, totaled over all MIN-101 dose groups, and as appropriate, totaled over all treatment arms, will be provided for age, BMI, weight in kilograms, and height in centimeters. Gender will be tabulated by dose group and overall. The BMI will be calculated and presented using the following formula: BMI = weight in kg/height in meters.

The number and percentage of patients who complete the double-blind treatment period and of patients who prematurely discontinue during the same period will be presented for each treatment arm and pooled across treatment arms for the Safety Population. The reasons for premature discontinuation from the double-blind treatment period as recorded on the termination pages of the eCRFs will be summarized (number and percentage) by treatment arm for the Safety Population. The percentage of premature discontinuations will be compared overall and for each discontinuation reason between treatment groups using the Fisher exact test.

The number and percent of patients with a current or historical presence of abnormal finding in medical history will be summarized by dose group and totaled over all dose groups.

## 10.4. Extent of Exposure and Treatment Compliance

#### **Investigational Product**

Exposure to double-blind treatment for the Safety Population during the double-blind treatment period will be summarized for treatment duration, calculated as the number of days from the date of the first dose of double-blind treatment taken to the date of the last dose taken, inclusive, for the double-blind treatment period. Descriptive statistics will be presented by treatment group.

#### **Prior and Concomitant Medications**

Prior medications are defined as any medication taken before the date of the first dose of double-blind treatment. Concomitant medications are defined as any medication taken on or after the date of the first dose of double-blind treatment.

Both prior medication use and concomitant medication use (during the double-blind treatment period) will be presented in data listings, and only concomitant medication will be summarized by the number and proportion of patients in each treatment arm receiving each medication within each therapeutic class for the Safety Population. Multiple medication use by a patient will only be counted once.

#### **Measurement of Treatment Compliance**

Dosing compliance for a specified period is defined as the total number of tablets actually taken by a patient during that period divided by the number of tablets prescribed during the same period multiplied by 100. The total number of tablets actually taken will be calculated from the study medication record. The number of tablets prescribed for a specific treatment period will be calculated by multiplying the number of days in that period by the number of tablets prescribed per day. Descriptive statistics for treatment compliance will be presented by treatment arm for each period between 2 consecutive visits when medication dispensation occurred, as well as for the entire double-blind treatment period.

#### 10.5. Efficacy Analyses

#### Primary Estimand

The primary estimand, the main clinical quantity of interest to be estimated in the study, is defined by the following 3 components:

**Population:** stable patients with schizophrenia with a predefined minimum PANSS negative symptom score.

Endpoint: change in PANSS Marder NSFS from baseline to the end of Week 12.

**Measure of Intervention:** the effect of the initially randomized treatment that would have been observed had all patients remained on their treatment throughout the double-blind phase.

The primary efficacy analysis will be based on the ITT Population. Baseline for efficacy is defined as values recorded at Visit 3 (Baseline).

Analyses of change from baseline will include only subjects who have both baseline and post-baseline data during the 12-week double-blind period.

All statistical tests will be 2-sided hypothesis tests performed at the 5% level of significance. All confidence intervals will be 2-sided 95% confidence intervals, unless stated otherwise.

Additionally, by-visit analyses will be done for all efficacy parameters using the MMRM and last observation carried forward (LOCF) approaches (described in Section 10.5.1), unless stated otherwise.

## 10.5.1. Primary Endpoint

The primary efficacy endpoint will be the change in the NSFS from baseline to Week 12 (the double-blind treatment period). This endpoint will be analyzed using MMRM with treatment arm (MIN-101 64 mg, MIN-101 32 mg, and placebo), pooled study center (by country or region based on enrollment), visit, and treatment arm-by-visit interaction as fixed effects, patient nested in treatment as random effect, and Baseline NSFS as covariate. An unstructured covariance matrix will be used to model the covariance of within-patient scores. The Kenward-Roger approximation (Kenward & Roger 1997) will be used to estimate denominator degrees of freedom. These analyses will be performed based on all post-Baseline scores using only the observed cases without imputation of missing values. Comparison against placebo will be performed with the MIN-101 64 mg and 32 mg doses.

The adjustment for multiplicity within the family of primary hypotheses will utilize the conventional Hochberg procedure for the purpose of reporting of results. This procedure will allow the null hypothesis of no treatment difference for both the 64 mg and 32 mg doses versus placebo to be rejected if largest p-value of comparing either of these 2 doses versus placebo is at or below 0.050. Otherwise, the lowest of these 2 p-values must be at or below 0.025 to allow for rejecting the null hypothesis for the representative dose.

The overall type I error rate for testing the 2 MIN-101 doses versus placebo for the primary and the key secondary endpoint will be controlled at the 2-sided 0.05 level. The primary family of hypotheses (corresponding to the primary endpoint) and the secondary family of hypotheses (corresponding to the key secondary endpoint, the change from Baseline in PSP Total score) will be tested in a sequential manner with suitable adjustment for multiplicity within the family of primary hypotheses and within the family of the secondary hypotheses such that a MIN-101 dose versus placebo null hypothesis contrast testing within the secondary family can be evaluated only when the same null hypothesis contrast in the primary family was rejected.

Sensitivity analyses of the primary endpoint will also be performed and will be detailed further in the SAP. These may include an ANCOVA model with factors for treatment and region and Baseline NSFS as a covariate. In this analysis, subjects without a NSFS at Week 12 will have an earlier postbaseline score imputed using the LOCF method. Other sensitivity analyses may also be performed to investigate the robustness of treatment estimates to the observed pattern of, and/or reason for, early withdrawals. Additional details will be provided in the SAP, including pre-specified sensitivity analyses under "non-ignorable" missing data mechanisms to assess the potential impact of the incorrect missing data assumption made for the primary analysis.

## 10.5.2. Secondary and Exploratory Endpoints

The change from Baseline in PSP total scores will be analyzed similarly to the primary endpoint with MMRM. The change from Baseline in CGI-S scores and

will be analyzed by means of an ANCOVA of ranked data, with treatment (MIN-101 64 mg, 32 mg, and placebo) as a factor, and Baseline CGI-S score as a covariate.

The change from Baseline for the remaining efficacy endpoints will be analysed similarly to primary endpoint.

The cumulative distribution function for the primary and key secondary endpoint will also be evaluated, as appropriate.

## 10.6. Interim Analyses

No formal interim analyses are planned for this study. Data from the double-blind 12-week phase are the primary focus of this study and will be analyzed once the last patient completes Visit 11 assessments and the database has been locked.

Additionally, an external DSMB will be established to review the safety data and formulate recommended decisions/actions in accordance with the charter of the DSMB.

#### 10.7. Pharmacokinetics

Individual plasma levels of MIN-101 and its metabolite(s) will be tabulated by MIN-101 dose with the corresponding day and time point. Descriptive statistics will be summarized by MIN-101 doses.

Population PK analysis of plasma concentration-time data of MIN-101 and its metabolite(s) will be performed using nonlinear mixed-effects modeling. Data will be combined with ongoing modeling dataset. Available patient characteristics (demographics, laboratory variables, etc.) will be tested as potential covariates affecting pharmacokinetic parameters. Post-hoc Bayesian individual estimates of PK parameters will be generated from the population PK analysis for potential use in exposure-response analysis.

Details will be given in a population PK analysis plan and results of the population pharmacokinetic analysis will be presented in a separate report.

## 10.8. Safety Analyses

The safety analysis will be performed for the double-blind treatment period and double-blind period using the Safety Population. Safety variables include AEs, clinical laboratory parameters, physical examination, vital signs, and ECG parameters.

For each safety parameter, the last assessment made before the first dose of double-blind treatment, or in case of ECG, the mean of the 3 triplicates (9 assessments) performed on Day -1, will be used as the baseline for all analyses of that safety parameter.

## 10.8.1. Adverse Events

The verbatim terms used in the eCRFs by investigators to identify adverse events will be coded using the Medical Dictionary for Regulatory Activities (MedDRA). All reported AEs with onset during the 12-week double-blind period (i.e., TEAE) will be included in the analysis. For each AE, the percentage of patients who experienced at least one occurrence of the given event will be summarized by treatment group.

Special attention will be given to those patients who died, or who discontinued treatment due to an AE, or who experienced an SAE (e.g., summaries, listings, and narrative preparation may be provided, as appropriate).

Adverse events of special interest are episodes of palpitations or abnormal heart rhythms episode of dizziness or syncope, and episode of seizure. Subjects with AEs of special interest may be presented separately.

An AE that occurs > 14 days after the date of the last dose of treatment will not be considered TEAE, but will be included in the patient data listings but not the summary tables.

# 10.8.2. Clinical Laboratory Tests

Laboratory data will be summarized by type of laboratory test. Reference ranges and markedly abnormal results (specified in the SAP) will be used in the summary of laboratory data. Descriptive statistics will be calculated for each laboratory analyte at Baseline and at each scheduled time point. Changes from Baseline results will be presented in pre- versus post-treatment cross tabulations (with classes for below, within, and above normal ranges). A listing of patients with any laboratory results outside the reference ranges will be provided. A listing of patients with any markedly abnormal laboratory results will also be provided.

## 10.8.3. Vital Signs

Descriptive statistics of body temperature, pulse, respiratory rate, and blood pressure (systolic and diastolic) values and changes from Baseline will be summarized at each scheduled time point. The percentage of patients with values beyond clinically important limits will be summarized. Clinically important limits will be defined in the SAP.

# 10.8.4. Electrocardiogram (ECG)

The effects on cardiovascular variables will be evaluated by means of descriptive statistics and frequency tabulations. These tables will include observed values and changes from Baseline values (mean of Day -1 ECG assessments will be used as Baseline) to allow detection of clinically relevant changes in individuals.

The ECG variables that will be analyzed are HR, RR, PR interval, QRS interval, QT interval, and QTcF interval. QTcF values will be tabulated for their absolute values and also tabulated relative to Baseline measurements in order to detect individual QTcF changes (ICH 2005).

Descriptive statistics of QTcF intervals and changes from Baseline will be summarized at each scheduled time point. The percent of patients with QTc interval > 450 msec, > 480 msec, or > 500 msec will be summarized as will the percent of patients with QTcF interval increases from Baseline of > 30 to 60 msec or > 60 msec.

For QTcF, an ANCOVA model by assessment times (visit and timepoint within visit) using the change from baseline (as dependent variable) with treatment arm (MIN-101 32 mg, MIN-101 64 mg, and placebo) as a factor, and Baseline value as covariate. Estimates for the difference at each assessment time for each dose group versus placebo, standard error of the mean, and the upper bound of the 2-sided 90% confidence intervals will be presented.

All important abnormalities in ECG waveform that are changes from the Baseline readings will be reported (e.g., changes in T-wave morphology or the occurrence of U-waves).

# 10.8.5. Physical Examination

Physical examination abnormalities will be listed. Observed and change from Baseline values of weight and waist circumference will be summarized descriptively.

# 10.8.6. Other Safety Parameters

Observed and changes from Baseline in AIMS, BARS, and SAS values will be summarized in tabular format showing descriptive statistics.

# 10.8.6.1. Sheehan Suicidality Tracking Scale

On the basis of the data collected using the Sheehan-STS, potential suicide-related events will be categorized by the investigator using the event report (page 2 of the scale).

Descriptive statistics of score values and changes from Baseline will be summarized at each scheduled time point. The endpoint of interest will be the proportion of patients with a suicide-related outcome.

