### FOR CLINICIAN USE ONLY

17. Missed appointm	ent - reason: subject died from a completed suicide?	0	100
18. Missed appointm	ent - reason: subject died, but not enough information to code as a suicide?	0	0
19. Missed appointm	ent - reason: subject died from cause(s) other than suicide?	0	0
20. Missed appointm	ent - reason: subject alive, but not available because of a suicide attempt?	0	4
21. Missed appointm	ent - reason: subject alive, but not available for known reasons other than suicide?	0	0
22. Missed appointm	ent - reason: subject alive, but not available, for uncertain reasons, or "lost to follow up"?	0	0
Total Scale Score	Add scores from Questions 1a (only if 1b is coded YES), + 2 through 11 + [the highest of 12 or any row of 16] + [the highest of 14 or any row of 15] + 17 + 20 [on page 3].		

I have reviewed the answers on Pages 1 and 2 with the patient.

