#### 5. STATISTICAL METHODS

Descriptive statistical methods will be used to summarize the data from this study, with hypothesis testing performed for selected endpoints. Unless stated otherwise, the term "descriptive statistics" refers to number of patients (n), mean, median, standard deviation (SD), minimum, and maximum for continuous data and frequencies and percentages for categorical data. All data collected during the study will be included in data listings. Unless otherwise noted, the data will be sorted by treatment group, patient number, and by date within each patient number.

The term 'treatment group' refers to the three treatment arms of this study: Placebo, 32 mg MIN-101, and 64 mg MIN-101.

All statistical testing will be two-sided and will be performed using a significance (alpha) level of 0.050 unless stated otherwise.

The statistical analyses will be conducted with the SAS® System version 9.4 or higher. All analyses will be performed using formal verification procedures. Specifically, results will be verified utilizing independent programming prior to issuance of the draft statistical report. All documents will be verified by the lead statistician to ensure accuracy and consistency of analyses.

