- O Scoring: Each item is scored on a 5-point Likert scale from 0 (not at all) to 4 (extremely). Data from the STS can be analyzed as individual item scores, a subscore for suicidal ideation (sum of scores from items 2, 3, and 4, plus score from item 5 if ≤ 1), a subscore for suicidal behavior (sum of scores from items 6, 7, and 8, plus score from item 5 if > 1) and the total scale score (calculated by add scores from Questions 1a (only if 1b is coded YES), + 2 through 11 + [the highest of 12 or any row of 16] + [the highest of 14 or any row of 15] + 17 + 20.
- Analysis: The two subscores and total scale score and change from Baseline will be summarized by treatment group and study visit. Complete data will be presented in patient data listings by treatment group and visit.
- The Readiness for Discharge Questionnaire (RDQ), assessed at hospital discharge after the
  initial dosing phase of the double-blind and open-label extension phases, will be presented in
  a listing by treatment and visit.

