## 7. CHANGES IN THE PLANNED ANALYSES

Relative to the protocol for MIN-101C07.v1.0, Amendment 2, dated 26 September 2018, there is a change in the conduct of the analysis. For the analyses planned for the EMA dossier, a multiple imputation approach will be used to impute values for missing primary (12-week NSFS) and key secondary (12-week PSP total score) endpoint data. Additionally, the PK/PD analysis discussed in the protocol will be part of the population PK analysis and reporting of the integrated data across multiple protocol, and a new PK/PD analyses were introduced in the Statistical Analysis Plan (SAP) to address exposure-response relationships, as outlined in Section 5.3.2.

Otherwise, the efficacy analyses were expanded from the protocol statistical plan but without additional deviations in the conduct of the study or the planned analysis being anticipated. Should any deviations from the analyses specified in the authorized SAP arise, such deviations will be documented in the final clinical study report.

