Table	14.3.5.2.2	Vital Signs Parameter Shifts from Baseline	Safety
Table	14.3.5.3.1.1	ECG Parameters and Change from Baseline by Time Point	Safety
Table	14.3.5.3.1.2	ECG Parameters and Change from Baseline by Time Point, 01 February 2020 Cutoff	Safety
Table	14.3.5.3.2.1	QTcF (msec) Values and Change from Baseline Relative to Predefined Thresholds of Clinical Significance	Safety
Table	14.3.5.3.2.2	QTcF (msec) Values and Change from Baseline Relative to Predefined Thresholds of Clinical Significance, 01 February 2020 Cutoff	Safety
Table	14.3.5.3.3.1	Effect of Treatment Arm on Changes in QTcF using ANCOVA	Safety
Table	14.3.5.3.3.2	Effect of Treatment Arm on Changes in QTcF using ANCOVA, 01 February 2020 Cutoff	Safety
Table	14.3.5.3.4.1	Patients with Clinically Significant ECG Abnormalities Occurring Post-Baseline	Safety
Table	14.3.5.3.4.2	Patients with Clinically Significant ECG Abnormalities Occurring Post-Baseline, 01 February 2020 Cutoff	Safety
Table	14.3.5.3.5.1	Patients with Potentially Clinically Significant ECG Abnormalities Occurring Post-Baseline	Safety
Table	14.3.5.3.5.2	Patients with Potentially Clinically Significant ECG Abnormalities Occurring Post-Baseline, 01 February 2020 Cutoff	Safety
Table	14.3.5.3.5.3	ECG Parameter Shifts from Baseline	Safety

T. 1.1		Description	Population
Table	14.3.6.1	Summary and Change from Baseline in Abnormal Involuntary Movement Scale (AIMS) Composite Movement Score and Severity Index, by Visit	Safety
Table	14.3.6.2	Summary and Change from Baseline in Barnes Akathisia Rations Scale (BARS) and Global Clinical Assessment of Akathisia, by Visit	Safety
Table	14.3.6.3	Summary and Change from Baseline in Simpson- Angus Scale (S-AS) Score, by Visit	Safety
Table	14.3.6.4	Summary and Change from Baseline in Sheehan Suicidality Tracking Scale (STS) Subscores and Total Scale Score, by Visit	Safety
Listings	•		•
Listing	16.2.1	Patient Disposition	Enrolled
Listing	16.2.2.1	Protocol Deviations	ITT
Listing	16.2.2.2	Inclusion/Exclusion Criteria	Enrolled
Listing	16.2.3	Inclusion in Analysis Populations	Enrolled
Listing	16.2.4.1	Demographic and Baseline Characteristics	ITT
Listing	16.2.4.2	Psychiatric and Medical History	ITT
Listing	16.2.4.3	Schizophrenia Characteristics at Baseline	ITT
Listing	16.2.4.4	CYP2D6 Genotyping	Enrolled
Listing	16.2.4.5	Concomitant Medication Blood Sampling	Enrolled
Listing	16.2.4.6	Urine Drug and Alcohol Screening	Enrolled
Listing	16.2.4.7	Hospital Admissions and Discharge/Continuation	ITT

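### The SAP omits, without declaring it, the protocol's suicidality endpoint: no planned output gives the share of patients per arm with a suicide-related outcome on the Sheehan-STS

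*Protocol*

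**What the plan says.** Protocol 10.8.6.1 plans two things for the Sheehan-STS. The first is descriptive statistics of scores and changes at each scheduled time point. The second is a patient-level endpoint: "The endpoint of interest will be the proportion of patients with a suicide-related outcome". The events behind it come from the investigator: "potential suicide-related events will be categorized by the investigator using the event report (page 2 of the scale". The term suicide-related outcome is not defined further. Protocol 2.1 lists the scale among the safety assessments.

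SAP 5.4.7 carries over only the first part: "The two subscores and total scale score and change from Baseline will be summarized by treatment group and study visit". It adds a listing: "Complete data will be presented in patient data listings by treatment group and visit". The matching table, 14.3.6.4, is titled "Summary and Change from Baseline in Sheehan Suicidality Tracking Scale (STS) Subscores and Total Scale Score, by Visit" in SAP 9.1 and appears under the same number in SAP 9.2. Listing 16.2.9.4 holds the assessments.

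SAP Section 7 names two changes from the protocol: multiple imputation for the EMA dossier, and the PK/PD analyses. It then says that the efficacy analyses were expanded "without additional deviations in the conduct of the study or the planned analysis being anticipated".

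**The concern.** The protocol singles out one suicidality measure as the one of interest, and the SAP gives it no derivation, method or table. The trial stops psychotropics before dosing and gives placebo to a third of patients. Protocol 1.5 describes worsening, and behaviour dangerous to the patient or to others, as the main risk of taking part. Protocol 1.4.2.3 records suicide attempt among the severe events of an earlier study of this drug. A reader of the report will therefore want to know how many patients per arm had a suicide-related outcome. Under the current SAP that number would have to be pieced together from listings, by a rule not fixed before unblinding.

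**Working it through.** **Protocol and SAP side by side**

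- Score statistics by time point: planned in protocol 10.8.6.1 and kept in SAP 5.4.7 and Table 14.3.6.4.
- Patient-level proportion: planned in protocol 10.8.6.1, absent from SAP 5.4.7 and from the table lists in SAP 9.1 and 9.2. The rating-scale tables run from 14.3.6.1 to 14.3.6.4 with no blanked row, so redaction does not explain the gap.
- Declaration: none in SAP Section 7.

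**Whether another planned output supplies the number**

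- *Score summaries.* SAP Section 5 defines descriptive statistics as "number of patients (n), mean, median, standard deviation (SD), minimum, and maximum for continuous data and frequencies and percentages for categorical data". The maximum shows the worst score at a visit, but not how many patients had an event.
- *Subscores.* SAP 5.4.7 builds ideation from items 2, 3 and 4 (plus item 5 if it is 1 or less), and behaviour from items 6, 7 and 8 (plus item 5 if above 1). In protocol Attachment 11, items 5 to 8 are method, means, place and date in mind. Preparation is item 12 and attempt is item 14. These two enter only the total, as does item 17 ("subject died from a completed suicide"), which is scored 0 or 100.
- *Visit windows.* SAP 3.3.7 summarises only the assessment closest to the target day when several fall in one window, including unscheduled and early-termination ones. The page 1 items cover the time since the last visit, so an assessment left out of the summary takes its interval with it.
- *Withdrawal.* Suicidal ideation or behaviour is a withdrawal criterion in protocol 9.3, so affected patients can drop out of later by-visit summaries.
- *Adverse-event tables.* These count by preferred term, and only what was reported as an adverse event. Suicidality is not an event of special interest (protocol 8.4, SAP 3.3.8), so no grouped count is planned there.
- *Listings.* These give patient detail but no rate by arm.

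**Illustration of size**

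The documents give no figure for suicidality to reproduce. Only the arm size is borrowed, from protocol 10.1: 100 / (1 − 0.40) = 166.7, rounded up to 167 per arm, and 3 × 167 = 501, as stated.

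Assumptions, not from the documents: k affected patients at a visit, each with total score s between 4 and 20; all others score 0; all 167 are assessed. The shift in the arm mean is k × s / 167.

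- k = 1: 4/167 = 0.024 to 20/167 = 0.120
- k = 3: 12/167 = 0.072 to 60/167 = 0.359

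SAP Section 8 reports means to the same number of significant digits as the parameter. For an integer score, read literally, all of these would print as 0.

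The proportion is k/167. The exact (Clopper-Pearson) limits are the 2.5th percentile of Beta(k, 168 − k) and the 97.5th percentile of Beta(k + 1, 167 − k).

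- k = 0: 0% (0% to 2.2%)
- k = 1: 0.6% (0.02% to 3.3%)
- k = 3: 1.8% (0.4% to 5.2%)

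The mean also mixes kinds of event. One completed suicide adds 100/167 = 0.60, the same as five patients scoring 20 each (5 × 20/167 = 0.60). The maximum would separate these two cases (100 against 20), but it would not give the counts of 1 and 5.

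**The case against.** A reader might infer that the SAP reports nothing but means, that rare events will stay hidden, and that suicidality will be judged on averages. The documents do not support that. The summaries include the maximum, and complete Sheehan-STS data are listed by patient. Treatment-emergent, serious and fatal adverse events are tabulated by arm, and a completed suicide during treatment would appear there. Reasons for discontinuation are tabulated by treatment group (SAP 5.1), and completed suicide is among the relapse terms in SAP Table 2.

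It is also fair to say that no event rate or score distribution is given. That nearly all scores will be zero is therefore a supposition, and a score of 4 for an affected patient is near the low end of the total. The proportion is a descriptive measure in a safety subsection, not an objective-level endpoint. The protocol does not ask for a between-arm risk difference.

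All of this limits the consequence. It does not fill the gap, because none of these outputs counts patients per arm with a suicide-related outcome on the scale. Ideation that the scale records but nobody reports as an adverse event would be in no count at all.

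**Conclusion.** The omission is real and undeclared: a safety measure that the protocol names has no analysis in the SAP. It is a consistency gap with a modest but real reporting consequence. Events would be partly visible through other outputs, but no event rate by arm on the scale would be available. The conclusion rests on comparing the two documents, taking the protocol text supplied to be the version against which Section 7 declares its changes. It does not depend on the illustration, whose event counts and score range are assumed. The protocol shares part of the gap, because it never says which items or event rows make up a suicide-related outcome.

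**What to change.** Add one table to SAP 5.4.7 and to the lists in 9.1 and 9.2: n (%) of patients per arm with at least one post-baseline suicide-related outcome at any time in the phase, counting unscheduled and early-termination assessments.

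Define the outcome by scale item and events-report row before unblinding, and show two lines:

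- behaviour: preparatory act (item 12 or rows of item 16), attempt (item 14 or rows of item 15, and item 20), completed suicide (item 17);
- ideation, from named page 1 items. Keep this line separate, because protocol 10.8.6.1 ties event categorisation to page 2, which covers attempts and preparation.

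State explicitly how items 1a/1b (accident with intent) and 13 (self-injury without intent to die) are handled. Derive the table from items and event rows, not from the SAP subscores. An exact confidence interval per arm is optional. Keep the score summaries as supportive.

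If the proportion is restored, Section 7 needs no entry for it. If the sponsor decides against restoring it, Section 7 should declare and justify the omission. The cost is one definition and one table per phase, from data already collected.
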